# Ocrelizumab—F. Hoffmann-La Roche Ltd

86/Protocol WA39085, Version 10

for safety reasons will not be replaced. Patients who withdraw from the study for reasons other than safety may be replaced in order to ensure that data from at least 6 evaluable patients per each cohort over 24 weeks are available to enable the dose selection decision.

# 4.6.3 Study Discontinuation

The Sponsor has the right to terminate this study at any time. Reasons for terminating the study may include, but are not limited to, the following:

- The incidence or severity of adverse events in this or other studies indicates a potential health hazard to patients
- Patient enrollment is unsatisfactory

The Sponsor will notify the investigator if the Sponsor decides to discontinue the study.

## 4.6.4 Site Discontinuation

The Sponsor has the right to close a site at any time. Reasons for closing a site may include, but are not limited to, the following:

- Excessively slow recruitment
- Poor protocol adherence
- Inaccurate or incomplete data recording
- Non-compliance with the International Council for Harmonisation (ICH) guideline for Good Clinical Practice
- No study activity (i.e., all patients have completed the study and all obligations have been fulfilled)

# 5. ASSESSMENT OF SAFETY

## 5.1 SAFETY PLAN

Ocrelizumab has not been investigated in children or adolescents with MS. The safety plan in this study is based on clinical experience with ocrelizumab in completed and ongoing studies. The sections below reflect safety data per the current Ocrelizumab Investigator's Brochure.

Parents/legal guardians/patients should be informed of the risks associated with taking ocrelizumab.

Several measures will be taken to ensure the safety of patients participating in this study. Eligibility criteria have been designed to exclude patients at higher risk for toxicities. Patients will undergo safety monitoring during the study, including assessment of the nature, frequency, and severity of adverse events. Compliance with the planned dosing schedule of ocrelizumab infusions is required unless an adjustment is necessary for safety reasons. During study visits when the ocrelizumab infusion is

interrupted for toxicity, all other study assessments should be performed as per the schedule of activities (see Appendix 1).

The anticipated important safety risks for ocrelizumab and recommendations for vigilance with signs and symptoms of particular safety events are summarized in the following sections.

Refer to the current version of the Ocrelizumab Investigator's Brochure for a complete summary of safety information.

# 5.1.1 Identified Risks and Adverse Drug Reactions Associated with Ocrelizumab Use

## 5.1.1.1 Infusion-Related Reactions

All CD20–depleting agents administered via IV, including ocrelizumab, have been associated with IRRs, which are related to the mechanism of action (i.e., cytokine release and/or other chemical mediators). IRRs may be clinically indistinguishable from Type 1 (IgE-mediated) acute hypersensitivity reactions (see Section 5.1.1.2).

Following the approved administration regimen (which includes the use of premedication prior to treatment with ocrelizumab to reduce frequency and severity of IRRs), symptoms of IRRs may occur during any ocrelizumab infusion, but have been more frequently reported during the first infusion. Physicians should alert patients and parent(s)/legal guardian(s) that IRRs can occur within 24 hours of the infusion. Across the RMS and PPMS trials, symptoms associated with IRRs included, but are not limited to, pruritus, rash, urticaria, erythema, throat irritation, oropharyngeal pain, dyspnea, pharyngeal or laryngeal edema, flushing, hypotension, pyrexia, fatigue, headache, dizziness, nausea, tachycardia, and anaphylaxis.

Patients should be observed for at least 1 hour after the completion of the infusion for any symptom of IRR. Patients should be informed about the possibility of delayed post-infusion symptoms and instructed to contact the study physician if he or she develops such symptoms.

Additional caution will be taken in this first study investigating ocrelizumab in children and adolescents by having the first infusion (Day 1 of Dose 1) scheduled in the morning to allow for a hospital stay with medical supervision and monitoring as needed, as long as possible.

For premedication see Section 4.3.3.

# **Managing Infusion-Related Reactions**

Infusion of ocrelizumab is administered under the close supervision of an experienced healthcare professional with access to appropriate medical support to manage severe reactions such as serious IRRs.

Patients who experience severe pulmonary events, such as bronchospasm or asthma exacerbation, must have their infusion interrupted immediately and permanently. After administering symptomatic treatment, monitor the patient until the pulmonary symptoms have resolved because initial improvement of clinical symptoms could be followed by deterioration.

Because transient hypotension may occur during ocrelizumab infusion, patients with low blood pressure should be monitored carefully. Patients with a history of congestive heart failure (New York Heart Association Class III/IV) were not studied.

In case of IRRs during any infusion, see recommendations in Section 4.3.4.

In the event of a suspected anaphylactic reaction during study treatment infusion, please refer to Appendix 6.

## 5.1.1.2 Infections

Infection is an identified risk associated with ocrelizumab treatment, predominantly involving mild to moderate respiratory tract infections. Non–disseminated herpes virus-associated infections, mostly mild to moderate, were also reported more frequently with ocrelizumab (approximately 5%–6%, simplex and zoster) than with comparators (approximately 3%).

During the controlled period of the pivotal trials, the proportion of patients with serious infections in RMS was lower in the ocrelizumab group (1.3%) than in the IFN beta–1a group (2.9%); in PPMS, the proportion of patients with serious infections, was similar in both groups: 6.7% in the placebo group compared with 6.2% in the ocrelizumab group.

Serious, opportunistic and fatal infections have occurred in patients with lupus and rheumatoid arthritis treated with ocrelizumab in Phase III clinical trials. Data from completed studies regarding infection risks with ocrelizumab treatment in these patient populations are provided in the current Ocrelizumab Investigator's Brochure.

No opportunistic infections were reported by any patient with MS treated with ocrelizumab during the controlled period of the pivotal trials.

In interventional clinical studies, there were no reports of hepatitis B reactivation in patients with MS treated with ocrelizumab, but was reported in 1 patient with rheumatoid arthritis treated with ocrelizumab. HBV screening should be performed in all patients before initiation of treatment with ocrelizumab as per local guidelines. Patients with active Hepatitis B virus should not be treated with ocrelizumab. Patients with positive serology should consult liver disease experts before start of treatment and should be monitored and managed following local medical standards to prevent Hepatitis B reactivation.

Delay ocrelizumab administration in patients with an active infection until the infection is resolved.

For PML see Section 5.1.2.

# 5.1.1.3 Impaired Response to Vaccination

After treatment with ocrelizumab for over 2 years in pivotal clinical trials, the proportion of adult patients with MS with positive antibody titers against *S. pneumoniae*, mumps, rubella, and varicella were generally similar to the proportions at baseline.

Physicians should review the immunization status of patients being considered for treatment with ocrelizumab. Patients who require vaccination should complete it at least 6 weeks prior to initiation of ocrelizumab.

In the randomized open-label Study BN29739, the humoral responses to tetanus toxoid, 23-valent pneumococcal polysaccharide (23–PPV), KLH neoantigen, and seasonal influenza vaccines were decreased in patients with RMS treated with ocrelizumab (compared with those patients not treated with ocrelizumab) at all timepoints measured. Nevertheless, patients with RMS who received ocrelizumab and were peripherally B-cell depleted were able to mount humoral responses, albeit decreased, to clinically relevant vaccines (tetanus toxoid, 23–PPV, influenza) and the neoantigen KLH. The results of the study confirm the current recommendation that patients should complete local vaccination requirements 6 weeks prior to initiation of ocrelizumab to obtain full effectiveness of the vaccines. In addition, for seasonal influenza vaccines, it is still recommended to vaccinate patients receiving ocrelizumab, as a humoral response to the vaccine, even if attenuated, can be expected.

Refer to the current Ocrelizumab Investigator's Brochure for details and see Section 3.4.7.2 and 5.1.5.

## 5.1.1.4 Decrease in Immunoglobulins

Treatment with ocrelizumab resulted in a decrease in total Igs over the controlled period of the studies, mainly driven by reduction in IgM. The proportion of patients with decrease in Igs below LLN increased over time and with successive dosing. Based on additional patient exposure, in cases of continuous decrease over time, a high risk of serious infection cannot be ruled out (see Section 5.1.1.5).

Patients with IgG and IgM below the exclusionary levels per Section 4.1.2.3 at screening will not be enrolled in the study. The investigator should closely monitor the patient's IgG and IgM levels during the study. If their levels decrease below the exclusionary levels following ocrelizumab treatment and require specific medical care or management, repeat dosing may be suspended until resolved or held indefinitely as per the judgement of the treating investigator.

#### 5.1.1.5 Serious Infections Related to Decrease in Immunoglobulins (Particularly in Patients Previously Exposed to Immunosuppressive or Immunomodulatory Drugs or with Preexisting Hypogammaglobulinemia)

Based on additional patient exposure, an association between decrease in Igs and serious infections with ocrelizumab treatment was observed and was most apparent for IgG. There was no difference in the pattern (type, latency, duration, outcome) of the serious infections reported in this subset of patients compared to the overall serious infections profile. In addition, risk factors for a subset of patients at higher risk of serious infections could not be identified.

# 5.1.1.6 Delayed Return of Peripheral B-cells

Treatment with ocrelizumab leads to rapid depletion of CD19 + B–cells in blood by 14 days post-treatment (first timepoint of assessment) and is an expected pharmacologic effect. This was sustained throughout the treatment period. The longest follow–up time after the last ocrelizumab infusion is from 51 patients in Study WA21493 and indicates that the median time to B–cell repletion (returned to baseline or LLN, whichever occurred first) was 72 weeks (range 27–175 weeks). Patients with prolonged B–cell depletion should be monitored until their B–cells have repleted. See the current Ocrelizumab Investigator's Brochure for further details.

# 5.1.2 Potential Risks Associated with Ocrelizumab Use

# 5.1.2.1 Malignancies including Breast Cancer

An increased risk of malignancy with ocrelizumab may exist. In controlled trials in adults with multiple sclerosis, malignancies—including breast cancer—occurred more frequently in ocrelizumab-treated patients. Breast cancer occurred in 6 of 781 females treated with ocrelizumab and none of 668 females treated with Rebif® or placebo. Patients should follow standard breast cancer screening as per local guidelines. The incidence of malignancies was within the background rate expected for an MS population.

Patients with an active malignancy or actively monitored for the recurrence of a malignancy should not be treated with ocrelizumab. For more detailed information and recent analyses, see the current Ocrelizumab Investigator's Brochure.

# 5.1.2.2 Progressive Multifocal Leukoencephalopathy

JCV infection, resulting in PML has been reported in patients treated with anti–CD20 antibodies, including ocrelizumab, and mostly associated with risk factors, such as patient population or polytherapy with immunosuppressants. The reporting rate with ocrelizumab has been approximately 1 case per 100,000 patients. Since a risk of PML cannot be ruled out, physicians should be vigilant for early signs and symptoms of PML, which can include any new onset, or worsening of neurological signs or symptoms as these can be similar to an MS relapse. If PML is suspected, dosing with ocrelizumab must be withheld. Evaluation of PML, including MRI scan, preferably with contrast

#### Ocrelizumab—F. Hoffmann-La Roche Ltd 91/Protocol WA39085, Version 10

(compared with pre-treatment MRI) confirmatory CSF testing for JCV DNA and repeat neurological assessments, should be considered. If PML is confirmed, ocrelizumab must be discontinued permanently (see Appendix 5).

PML is a potentially fatal neurological condition linked to reactivation of a polyomavirus, JCV, and active viral replication in the brain. Polyomavirus infection is acquired in childhood, and up to 80% of adults demonstrate serologic evidence of past infection. Reactivation of JCV replication with transient viremia or viruria unassociated with clinical symptoms may occur spontaneously in healthy persons. Less frequently, CNS symptoms associated with active viral replication in brain tissue are observed. The clinical syndrome is significantly more frequent among immune-suppressed patients. There is no known treatment or cure for PML. Treatment considerations are discussed in the medical literature (Calabrese et al. 2007).

Physicians should consider the diagnosis of PML in any patient presenting with new and/or progressive neurologic deficits localized to the cerebral cortex, such as cortical symptoms/signs, behavioral and neuropsychological alteration, retrochiasmal visual defects, and hemiparesis, and cerebellar symptoms/signs (e.g., gait abnormalities and limb incoordination), at each visit. Guidance for diagnosis of PML is given in Appendix 5.

PML should be reported as a serious adverse event (with all available information) with immediate notification of the Sponsor's Medical Responsible and the Medical Monitor.

In this study, comprehensive neurologic assessments will be performed every 24 weeks at the regular site study visits. Patients will be required to undergo a neurologic examination for calculation of an EDSS score every 24 weeks. This requires that FSS also be determined. The examination to calculate the FSS includes cognitive, visual, and motor assessments; the neurologic systems most often affected by PML; as well as assessments of other neurologic systems.

On the eCRF, the investigator will record the presence or absence of neurological deficits localized to the cerebral cortex (e.g., cortical symptoms/signs, behavioral and neuropsychological alteration, retrochiasmal visual defects, and hemiparesis) and cerebellar symptoms/signs (e.g., gait abnormalities and limb incoordination) at each visit. Presence of such neurological findings will be recorded as adverse events. If a diagnosis for the deficits is identified, the symptoms should be replaced by the diagnosis in the Adverse Event eCRF.

In addition to the neurologic evaluation performed every 24 weeks at site, there will be regular study visits (site or MN visits, as applicable) in between; furthermore, patients will undergo a telephone interview every 4 weeks between the study visits by site personnel familiar with the patient(s). The purpose of this interview is to identify new or worsening neurological symptoms that warrant an unscheduled visit. Parents/legal guardians of

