# 5.2.1 Adverse Events

According to the ICH guideline for Good Clinical Practice, an adverse event is any untoward medical occurrence in a clinical investigation subject administered a pharmaceutical product, regardless of causal attribution. An adverse event can therefore be any of the following:

• Any unfavorable and unintended sign (including an abnormal laboratory finding), symptom, or disease temporally associated with the use of a medicinal product, whether or not considered related to the medicinal product

- Any new disease or exacerbation of an existing disease (a worsening in the character, frequency, or severity of a known condition), except as described in Section 5.3.5.11
- Recurrence of an intermittent medical condition (e.g., headache) not present at baseline
- Any deterioration in a laboratory value or other clinical test (e.g., ECG, X-ray) that is associated with symptoms or leads to a change in study treatment or concomitant treatment or discontinuation from study drug
- Adverse events that are related to a protocol-mandated intervention, including those that occur prior to assignment of study treatment (e.g., screening invasive procedures such as biopsies)

New or worsening neurologic symptoms not considered MS-related should be recorded on an Adverse Event eCRF, and the Medical Monitor should be informed.

Adverse events will be recorded on the Adverse Event eCRF. For clinical relapses and IRRs, a Specific Adverse Event eCRF triggered by an appropriate entry on the main Adverse Event eCRF will be used. The reporting requirements will be the same as for any other adverse event.

Further information related to clinical relapses will be recorded only on a prespecified eCRF MS Relapse eCRF. Signs, symptoms, and severity of IRRs will also be recorded on a prespecified IRR eCRF.

B-cell depletion is the expected outcome of ocrelizumab treatment and is not an adverse event. However, patients may be at risk for infections, and particular attention should be directed toward early identification and treatment of infections (see Section 5.1.1.2).

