# 5.3.5.10 Preexisting Medical Conditions

A preexisting medical condition is one that is present at the screening visit for this study. Such conditions should be recorded on the General Medical History and Baseline Conditions eCRF.

A preexisting medical condition should be recorded as an adverse event only if the frequency, severity, or character of the condition worsens during the study. When recording such events on the Adverse Event eCRF, it is important to convey the concept that the preexisting condition has changed by including applicable descriptors (e.g., "more frequent headaches").

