# 5.3.5.11 Lack of Efficacy or Worsening of Multiple Sclerosis

Events that are clearly consistent with the expected pattern of progression of the underlying disease should not be recorded as adverse events. Clinical relapses should be captured on the MS Relapse eForm (see Section 5.2.1,). These data will be captured as exploratory assessment data only. However, every effort should be made to document progression through use of objective criteria. If there is any uncertainty as to whether an event is due to disease progression, it should be reported as an adverse event.

Medical occurrences or symptoms of deterioration that are judged by the investigator to have unexpectedly worsened in severity or frequency or changed in nature at any time during the study should be recorded as an adverse event.

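### Section 5.1.2.2 makes the mere presence of a cortical or cerebellar deficit an adverse event, so a standing deficit counts as 0 or 1 adverse event depending on which section a site follows

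*Combined protocol and SAP*

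**What the plan says.** Section 5.1.2.2 asks the investigator to mark on the eCRF, at each visit, whether cortical deficits (hemiparesis and retrochiasmal visual defects are among the examples) and cerebellar signs (gait abnormality, limb incoordination) are present or absent. Two instructions follow: "Presence of such neurological findings will be recorded as adverse events", and "If a diagnosis for the deficits is identified, the symptoms should be replaced by the diagnosis in the Adverse Event eCRF". Neither mentions baseline status or MS.

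Other sections set narrower rules:

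- Section 5.3.5.10: a condition already present at screening becomes an adverse event only "if the frequency, severity, or character of the condition worsens during the study".
- Section 4.5.5: abnormalities found at the baseline physical examination go to the medical history form. Later, new abnormalities or clinically significant worsening are recorded as adverse events if appropriate.
- Section 5.3.5.11: "Events that are clearly consistent with the expected pattern of progression of the underlying disease should" not be recorded as adverse events. Uncertain cases and unexpected worsening are still recorded.
- Section 5.3.5.5: an event that persists without resolving is entered once.

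Section 6.6 reports adverse events in two ways: as the number of patients with at least one treatment-emergent occurrence, and as a rate per 100 patient-years with an exact Poisson interval.

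**The concern.** Hemiparesis, gait ataxia and limb incoordination are ordinary MS deficits, and Section 4.1.1.2 admits patients with EDSS 0 to 5.5. Section 4.5.14 builds the EDSS from pyramidal, cerebellar, visual, cerebral and ambulation findings, which overlap with what the PML item screens. A child may therefore enter with a stable sign that the investigator marks as present at every visit. Section 5.1.2.2 taken literally makes that sign an adverse event; Sections 4.5.5 and 5.3.5.10 do not. A deficit that accrues slowly and is clearly expected MS progression meets the same conflict with Section 5.3.5.11.

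Occurrence and severity of adverse events is the first-listed secondary safety endpoint, summarised by cohorts of about six. Sites that follow different sections would report different counts for the same clinical state. Version 10 added the exposure-period definition and analysis considerations to Section 6.6 at a regulator's request, so the numerator of the new rate should be unambiguous.

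**Working it through.** The plan states no figure for this point, so there is none to reproduce. The check is a comparison of the rules, followed by an illustration of size.

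**Rules applied to a cerebellar sign present at baseline and unchanged**

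| Section | Adverse event entries |
|---|---|
| 5.1.2.2, read literally | 1 (presence is the trigger; 5.3.5.5 then limits it to one entry) |
| 5.3.5.10 | 0 (not worsened) |
| 4.5.5 | 0 (baseline abnormality, neither new nor worsened) |

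**Rules applied to a deficit that accrues slowly and is clearly expected MS progression**

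| Section | Adverse event entries |
|---|---|
| 5.1.2.2, read literally | 1 |
| 5.3.5.11 | 0, unless the worsening is unexpected or its cause uncertain |

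**Does Section 6.6 remove the difference?** Not reliably. The incidence count uses the term treatment-emergent, which the protocol does not define. The rate per 100 patient-years covers all adverse events, without that term.

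**Illustration for one cohort**

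Inputs: 6 patients per cohort (Section 6.1); 288 weeks of treatment plus 104 weeks of safety follow-up on the visit schedule = 392 weeks. Assumptions: one child has one unchanged baseline deficit, and all six complete follow-up.

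- Incidence for that event: 0/6 = 0% against 1/6 = 16.7%, Clopper-Pearson 95% CI 0.4% to 64%.
- Patient-years: 6 × 392 / 52.18 = 45.1.
- Rate: 0 / 45.1 = 0 against 1 / 45.1 = 2.2 per 100 patient-years.

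**Illustration for the minimum enrolment of 12**

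Patient-years: 12 × 392 / 52.18 = 90.2. Exact Poisson 95% limits are in brackets.

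| Children with such a deficit | Under 5.3.5.10 and 5.3.5.11 | Under 5.1.2.2 | Patient incidence |
|---|---|---|---|
| 1 | 0 (0 to 4.1) per 100 | 1.11 (0.03 to 6.18) per 100 | 0% against 8.3% |
| 3 | 0 (0 to 4.1) per 100 | 3.33 (0.69 to 9.72) per 100 | 0% against 25% |

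With 36 patients (270.5 patient-years) and one affected child, the rate is 0 against 0.37 per 100.

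**Scale against the overall rate.** The adult RMS figures in Section 1.2.4.2 (4194 events, 825 patients, 96 weeks assumed complete) give 4194 / (825 × 96 / 52.18) = 276 per 100 patient-years. One extra entry in a cohort of six is 2.2 / 276 = 0.8% of that.

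**The case against.** The strongest reply is that context supplies the limit. Earlier in Section 5.1.2.2 the protocol says "Physicians should consider the diagnosis of PML in any patient presenting with new and/or progressive neurologic deficits localized to the cerebral cortex", followed by nearly the same list of signs, and the later text on telephone interviews and follow-up also speaks of new or worsening symptoms. On that reading the findings meant are already new or progressive, and Sections 4.5.5 and 5.3.5.10 deal with stable ones. This may well be the intent. But that wording governs when to consider PML. The recording sentence refers back to the presence-or-absence item, which carries no such limit, and it has no cross-reference to Sections 5.3.5.10 or 5.3.5.11.

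The reply on size mostly stands. One entry is under 1% of a total rate of the adult magnitude. Overall patient incidence may not move, since 83.3% of adults with RMS had some adverse event. Individual listings would let a reader see the extra entry in a cohort of six. The effect is on the specific neurologic event, not on the overall safety picture.

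Three stronger readings are tempting, and the documents do not support them:

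- A reader might infer that a standing deficit becomes a new adverse event at every visit. Section 5.3.5.5 allows one entry for a persistent event; only an event that resolves and returns is entered again.
- A reader might infer that Section 5.2.1 keeps MS-related deficits out, because it says "New or worsening neurologic symptoms not considered MS-related should be recorded on an Adverse Event eCRF". That requires entry of non-MS symptoms; it does not bar MS-related ones. The same section says "For clinical relapses and IRRs, a Specific Adverse Event eCRF triggered by an appropriate entry on the main Adverse Event eCRF will be used", and Section 5.3.5.2 agrees, so relapses do pass through the adverse event form.
- A reader might infer that extra entries would hide new deficits from the PML screen. Nothing in the documents shows this.

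**Conclusion.** The contradiction is real and narrow. As worded, Section 5.1.2.2 conflicts with Sections 4.5.5 and 5.3.5.10 for stable baseline deficits, and with Section 5.3.5.11 for deficits clearly due to expected MS progression. Each such deficit is 0 or 1 adverse event according to the section followed. In a cohort of six, one affected child shifts that event by 16.7 percentage points and its rate by about 2.2 per 100 patient-years. These sizes assume complete follow-up and one affected child; the EDSS limit shows that such signs are possible at entry, not how often they occur. Section 6 makes every analysis descriptive, so neither type I error nor power is affected. The point deserves correction because a stated rule can give the wrong count and the remedy is cheap.

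A related inconsistency should be settled at the same time. Sections 5.2.1 and 5.3.5.2 enter relapses through the main adverse event form, while Section 5.3.5.11 says of relapse data: "These data will be captured as exploratory assessment data only". The plan should state whether a relapse counts in the Section 6.6 tables.

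**What to change.** Replace the recording sentence in Section 5.1.2.2 with:

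*Such findings that are new or have worsened since the baseline examination will be recorded as adverse events, subject to Sections 5.3.5.5, 5.3.5.10 and 5.3.5.11; if it is uncertain whether a finding is due to MS progression, it is recorded as an adverse event.*

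Do not add a general exclusion for findings attributed to MS. Section 5.3.5.11 still requires unexpected worsening to be recorded, and Section 5.1.2.2 itself notes that early PML can resemble a relapse, so such an exclusion would create a new conflict and narrow the screen.

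Keep the presence-or-absence item at each visit and list it by patient against baseline. If the sponsor wants broader capture for the PML screen, it should say so as an explicit exception to Sections 5.3.5.10 and 5.3.5.11 and tabulate those entries separately. Reconcile Sections 5.2.1 and 5.3.5.2 with Section 5.3.5.11 on whether relapses count as adverse events.

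The cost is one sentence in Section 5.1.2.2, a matching line in the eCRF completion guidance, and a short clarification on relapses. No surveillance data are lost, because the presence item still captures every deficit.
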